**Title: Enhancing Spatial Navigation using Non-Invasive Brain Stimulation
NCT01958437**

PI: [name], ABPP/CN

Objectives: Remembering how to travel from one location to another is critical in everyday life, yet this vital ability declines with normal aging and can be further affected by conditions that disproportionately affect older adults, such as progressive dementia. Human and animal research has shown that two distinct memory systems interact during navigation. The first, referred to as allocentric navigation, is flexible and uses spatial knowledge of key features or landmarks to develop and use a mental map of the environment. This approach involves brain regions that are critical for new learning and memory but that decline with age. The second, referred to as egocentric navigation, is inflexible and relies on “habit” memories that link specific features with specific directions. This approach relies on brain regions that are critical for “automatic” responses and that are relatively unaffected by age.

The main problem is that allocentric navigation declines with age and is accompanied by increased dependence on egocentric navigation. This change increases the risk of becoming disoriented or “lost” when traveling in unfamiliar areas or even when traveling new routes in familiar areas. Therefore, **the main goal** of this project is to examine whether non-invasive brain stimulation, specifically transcranial direct current stimulation, can improve allocentric navigation in cognitively intact older adults and those who have been diagnosed with mild cognitive impairment (MCI) – a clinical precursor to Alzheimer’s type dementia.

Specific Aims/Hypotheses:

Specific Aim 1: Examine the effects of high definition tDCS (HD-tDCS) on both allocentric and egocentric memory test performance. We predict that participants will perform more accurately following active HD-tDCS when compared to sham HD-tDCS.

Specific Aim 2: Examine the neurophysiologic response to HD-tDCS using fMRI. We predict that active HD-tDCS will increase BOLD signal in a behaviorally meaningful way regardless of diagnostic group (i.e., healthy control vs. MCI). Critical questions about the restorative vs. compensatory effects of tDCS in those with MCI will be examined by contrasting BOLD signal change between the groups

Methodology

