We have further applied a 'data-driven' approach based on Graph Theory to analyze the functional connectivity network before and after the intervention. We've used Power's 264 anatomical coordinates to segment the brain into 264 ROIs. We included additional medial temporal and subcortical ROIs. Each ROI was defined as a 5 mm sphere centered around these coordinates. A binary grey matter mask was created through the segmentation procedure in VBM8 and the threshold probability of 0.6 (as suggested by Zalesky et. al.) was used to overlay on the normalized resting state images. The average time course signal of the grey matter voxels in each ROI was measured. Pearson's correlation between the signal time course of all possible pairs of ROIs was conducted. Correlation weights that failed the false discovery rate (FDR) threshold at $p < 0.05$ were discarded. Graph parameters, including total functional connections, network strength, and network cost were calculated.

Within each group (HC and MCI), we will use the active > sham contrast to identify regions that differ as a result of HD-tDCS. Correlations between behavioral performance (e.g., accuracy in CM) and BOLD signal will also be calculated to determine whether the altered BOLD signal is behaviorally meaningful. Because we expect functional reorganization throughout the brain within both groups as a result of HD-tDCS, we intend to use connectivity analyses to examine changes in the connectivity between the parietal cortex and the remainder of the brain.

Exploratory between group analysis will use two primary contrasts. 1) HC sham > MCI sham – which will identify disease-related differences in activation between the groups; 2) HC active > MCI active – which will examine whether the tDCS-related changes are greater in one group than the other. Taken together, these contrasts will also clarify whether tDCS restores functioning in brain regions involved in "normal" (i.e., age appropriate) navigation or whether it allows MCI patients to recruit alternative brain regions in a compensatory manner.

Additional analyses will be performed as necessary in order to fully characterize the nature of tDCS-related changes.

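### The restoration-versus-compensation inference names no comparison of stimulated MCI patients with unstimulated controls, so normalisation can be understated or missed if controls also respond

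*Combined protocol and SAP*

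**What the plan says.** The closing paragraphs of the imaging analysis, under Statistical Design, define two between-group contrasts and label them exploratory. The first is "1) HC sham > MCI sham – which will identify disease-related differences in activation between the groups". The second is "2) HC active > MCI active – which will examine whether the tDCS-related changes are greater in one group than the other". The inference drawn from the pair follows: "Taken together, these contrasts will also clarify whether tDCS restores functioning in brain regions involved in" normal, age-appropriate navigation, or whether patients draw on alternative regions as compensation. The text does not say which pattern of results would count as either.

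Three other parts of the document bear on this:

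- The same section plans a within-group analysis: "Within each group (HC and MCI), we will use the active > sham contrast to identify regions that differ as a result of HD-tDCS".
- Specific Aim 2 states: "We predict that active HD-tDCS will increase BOLD signal in a behaviorally meaningful way regardless of diagnostic group". The analysis section adds that reorganisation is expected in both groups.
- Task analysis describes a mixed ANOVA with task, session and group effects, navigation regions of interest, and extracted beta values. It does not name a comparison of MCI active with HC sham. Neither does the closing sentence that allows additional analyses.

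**The concern.** Restoration means that stimulated patients move towards what controls do without stimulation. In this crossover, HC under sham is the nearest measure of that state. The only between-group contrast that contains stimulated patients sets them against stimulated controls, and the plan itself expects stimulation to move those controls. That contrast therefore combines two responses, and a residual HC > MCI difference need not mean that patients still fall short of normal.

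Compensation has a similar problem. It means that patients recruit regions outside normal navigation, which would appear as MCI exceeding HC. Both contrasts are written in the opposite direction, so as written they would not display it.

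Aim 2 presents restoration versus compensation as a critical question for MCI. If the listed contrasts cannot separate the relevant patterns, the imaging data could be collected as planned and the question still be answered wrongly or not at all.

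**Working it through.** The documents give no effect size, power or sample-size calculation for these contrasts, so there is no figure to reproduce. The check is contrast algebra followed by an illustration.

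**Definitions.** For one region:

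- C1 = HC sham − MCI sham (the sham gap)
- C2 = HC active − MCI active
- dHC and dMCI = active minus sham within each group

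**Step 1: what C2 contains.** C2 = (HC sham + dHC) − (MCI sham + dMCI) = C1 + dHC − dMCI.

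**Step 2: full normalisation.** MCI active = HC sham means dMCI = C1. Then C2 = C1 + dHC − C1 = dHC, so the contrast shows only the controls' response. The unnamed contrast, HC sham − MCI active = C1 − dMCI, is 0 whatever controls do.

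**Step 3: numbers.** Assume a sham gap of 0.8 SD.

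| dHC | dMCI | C1 | C2 | HC sham − MCI active |
|---|---|---|---|---|
| 0 | 0.8 | 0.8 | 0.0 | 0.0 |
| 0.2 | 0.8 | 0.8 | 0.2 | 0.0 |
| 0.4 | 0.8 | 0.8 | 0.4 | 0.0 |
| 0.8 | 0.8 | 0.8 | 0.8 | 0.0 |
| 1.2 | 0.8 | 0.8 | 1.2 | 0.0 |
| 0 | 0 | 0.8 | 0.8 | 0.8 |
| −0.8 | 0 | 0.8 | 0.0 | 0.8 |

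The first five rows are full normalisation. Row 1 is read correctly from C1 and C2, and rows 2 and 3 look like partial restoration. Row 4 has the same C1 and C2 as row 6, where stimulation does nothing in either group. Row 7 is the reverse error: the gap closes because controls fall. It runs against the direction that Aim 2 predicts and is shown only for completeness.

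**Step 4: how often C2 would be significant under full normalisation.** Power = 1 − Φ(z − C2/√(2/n)), for a single region and the HC > MCI direction. The documents give only a ceiling of 60 participants. The group sizes of 30 and 20 are assumptions, and imaging numbers may be lower because people who cannot have MRI may still enrol.

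| dHC as share of the 0.8 SD gap | n = 30, one-sided 0.05 | n = 20, one-sided 0.05 | n = 30, one-sided 0.001 |
|---|---|---|---|
| 0 | 0.05 | 0.05 | 0.001 |
| 0.25 | 0.19 | 0.16 | 0.010 |
| 0.5 | 0.46 | 0.35 | 0.062 |
| 1.0 | 0.93 | 0.81 | 0.503 |

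Worked entry: with n = 30 and dHC = 0.4, √(2/30) = 0.258, 0.4/0.258 = 1.55, and 1 − Φ(1.645 − 1.55) = 0.46.

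At dHC equal to the gap, C2 = C1, so the last row also gives the chance of detecting the sham gap itself. At 0.001, the strict end of the plan's uncorrected threshold range, that chance is only about one half. A non-significant contrast at that threshold is therefore weak evidence that a gap has closed. With other assumed gaps, n = 30, one-sided 0.05 and dHC at half the gap, the probability that C2 is significant is 0.25 (gap 0.5 SD) and 0.62 (gap 1.0 SD).

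**Step 5: would the interaction serve instead?** The second contrast is described as testing whether the change differs between groups. That quantity is C2 − C1 = dHC − dMCI. It is 0 when both groups rise equally, including row 4, so it does not test normalisation either.

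**The case against.** The strongest reply is that the plan has no decision rule to fault. It says the contrasts together will clarify the question, and the sham contrast is one of them. A reader might infer that complete normalisation in MCI would be reported as no restoration whenever Aim 2's prediction holds. The documents do not support that. Aim 2 predicts an increase in each group; it does not predict equal increases or name a region where both occur. A reading of no restoration needs controls to rise by about the whole sham gap in the same region.

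Second, the missing quantity can be built from planned pieces: C1 − (MCI active − MCI sham) = HC sham − MCI active. The within-group MCI contrast also shows which regions respond, and setting it beside C1 shows whether they are deficit regions. This stands in part. The plan does not tie that contrast to the restoration inference, and a rise alone does not show how far patients remain from normal.

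Third, the wording is mainly about which regions are active, so taking HC sham as the benchmark level is an interpretation. It is a reasonable one, since the plan refers to normal navigation and expects stimulated controls to change.

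Fourth, the analysis is exploratory, and no behavioural or safety conclusion depends on it. That limits the consequence.

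Fifth, MCI active versus HC sham differs in both diagnosis and stimulation, and a null result would not prove normalisation. Both statements are true, and they govern how the added contrast should be reported.

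**Conclusion.** The point holds in a conditional form. The plan rests a stated inference on two contrasts, neither of which compares stimulated patients with unstimulated controls, and both run in one direction only. If controls respond, as the plan expects, the active-active contrast under full normalisation equals the control response, so normalisation in MCI can be understated or, with a control response near the whole gap, missed. If controls do not respond in the region, the planned contrasts read correctly.

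The algebra needs no assumption beyond the definition of full normalisation as MCI active = HC sham. The sizes and probabilities rest on assumed gaps, control responses and group sizes, because the documents give none of these for the contrasts. The documents also do not support discarding the active-active contrast: it matches the groups on condition and remains informative when read with the others. This is a cheap improvement to an exploratory analysis of a question that the aims treat as critical.

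**What to change.** Keep both planned between-group contrasts. Add MCI active versus HC sham, tested in both directions, and read it together with the already planned MCI active > sham contrast. State in the plan:

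- **Restoration:** in regions with a sham deficit (HC sham > MCI sham), MCI active exceeds MCI sham and the remaining distance to HC sham shrinks. Report that distance with its confidence interval; do not infer closure from non-significance.
- **Compensation:** MCI active exceeds both MCI sham and HC sham in regions outside the HC sham navigation map.
- The restoration conclusion does not rest on HC active > MCI active alone.

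The cost is one second-level contrast, with no new data collection, and a few sentences of text. The downside is one more exploratory contrast. Because it differs in both diagnosis and stimulation, it should be described as a distance to the unstimulated reference, not as an effect of either factor.

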Participants: We will enroll up to 60 older adults (age 50+), who are right handed and MRI compatible, from the VA Ann Arbor Healthcare System, the University of Michigan Alzheimer’s Disease Center (MADC), and the surrounding community. Enrollment is open to participants regardless of race, gender, or social status.

Inclusion criteria: Patients will receive a diagnosis of MCI based on the Albert et al. (2011) criteria. Specifically, patients will **1)** report a subjective decline in memory (report can also be provided by an informant), **2)** demonstrate objective impairment in memory (based on Neuropsychological testing), and **3)** remain independent in activities of daily living. All patients will be stable on nootropic medications for at least 1-2 months prior to study initiation.

By definition, healthy controls (HC) will be free of objective memory test impairment (i.e., all scores within normal limits on the standardized testing protocol below).

Exclusion criteria: A history of **1)** contributory other neurological (e.g., epilepsy, moderate - severe traumatic brain injury) or medical conditions that are known to affect cognitive functioning; **2)** significant psychiatric conditions (e.g., moderate - severe depression, bipolar disorder, schizophrenia); **3)** sensory impairments that limit the ability to take part in the study; **4)** a significant history or current use of alcohol or drug abuse/dependence. Participants will also be screened to ensure MRI compatibility (assessed using the guidelines set forth by the American College of Radiology); some of the criteria for which are also reasons for excluding someone from tDCS (e.g., metallic or electronic implants). Eligible participants who cannot undergo MRI will be enrolled in the study and will complete only the stimulation and behavioral portions of the study. We have successfully used this same approach in our previous RCTs.

Recruitment: Participants will be recruited from both the VA Ann Arbor Healthcare system and the University of Michigan Alzheimer’s Disease Center. The primary recruitment source of MCI patients at the VA will be the Neuropsychology Clinic while HC will be recruited from the general VA community via postings/flyers in approved areas. The primary recruitment site for non-Veterans will be the University of Michigan Alzheimer’s

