constructed a mixed ANOVA model to test the influence of the aforementioned variables. Second-level maps were initially thresholded at whole-brain $p < .01$ to $.001$, uncorrected (extent threshold, $k = 10$). In addition to whole brain analysis, we also created a mask from activations seen in the whole brain analysis of task main effects (voxel-wise FWE $p < .05$) for use in group analyses of session effects. Specific regions of interests (ROIs) were also utilized, selected based on prior work (Hampstead et al., 2014) in regards to spatial navigation and derived from the Anatomical Automatic Labeling software (Tzourio-Mazoyer et al, 2002). These ROIs included hippocampus, superior parietal lobule, and caudate (all small volume corrected at voxel-wise FWE $p < .05$). Beta values of surviving brain activations were extracted and analyzed with ANOVA with significance threshold set at $p < .05$.

Resting state analysis

Resting state functional connectivity was first examined using a region of interest (ROI) "seed" at the stimulation site, right superior parietal lobule (rSPL), using a 10 mm radius spheres centered at MNI: (24, -60, 60). Pearson product-moment correlation coefficients were calculated between the average BOLD time course in the seed region and all other voxels in the brain. Each correlation resulted in a 3D correlation coefficient image (r-image). R-images were then transformed to z scores using a Fisher r to z transformation. Z score images from the individual functional connectivity analyses were entered into second-level random effects analyses (factorial ANOVA and t-tests) implemented in SPM8.

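### The two group maps given the restoration question measure neither change nor the remaining gap, so a sham gap that is missing under active stimulation is not evidence of normalisation

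*Combined protocol and SAP*

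**What the plan says.** Specific Aim 2 sets the question: "Critical questions about the restorative vs. compensatory effects of tDCS in those with MCI will be examined" by contrasting BOLD signal change between the groups.

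The end of the statistical section, after the resting-state methods, says how. "Exploratory between group analysis will use two primary contrasts". The first is "HC sham > MCI sham – which will identify disease-related differences in activation between the groups". The second is "HC active > MCI active – which will examine whether the tDCS-related changes are greater in one group than the other". The plan then concludes: "Taken together, these contrasts will also clarify whether tDCS restores functioning in brain regions involved in" age-appropriate navigation, or whether it lets MCI patients recruit other regions.

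Other relevant analyses are planned. The preceding paragraph says: "Within each group (HC and MCI), we will use the active > sham contrast to identify regions that differ as a result of HD-tDCS", and adds correlations of BOLD signal with behaviour. Under Task analysis there is a mixed ANOVA on task, session and group. That section also has a mask built from task main effects, a priori ROIs (hippocampus, superior parietal lobule, caudate), and the thresholds: "Second-level maps were initially thresholded at whole-brain" p<.01 to .001, uncorrected, extent 10 voxels.

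On size, the Participants paragraph says only "We will enroll up to 60 older adults". It gives no HC:MCI split, and it lets people who cannot have MRI take part without scans. The document gives no effect size, equivalence margin, confidence-interval criterion or definition of restoration.

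**The concern.** To say that stimulation restores function is to claim two things: that activation in MCI changed under stimulation, and that what remains of the difference from normal is small. The two named contrasts address neither. Each compares the groups within one condition. The second is described as examining tDCS-related change but has no sham term. Neither is accompanied by an interval for the gap.

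Read as a pair, they can point to restoration in one way only: a region appears in the sham map and drops out of the active map. Dropping out of a thresholded map is a non-significant test, which a small study often produces when the gap is unchanged.

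A second problem follows from using the sham map to find the disease-related regions. Regions chosen because their sham gap came out large will tend to show a smaller gap in the other session by regression to the mean, even if stimulation does nothing.

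At stake is a report that tDCS restored MCI brain function when it had no effect, on a question that Aim 2 calls critical.

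**Working it through.** The plan gives no power or sample-size figure to reproduce, so this is an illustration.

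**From the document:** at most 60 participants; active and sham in the same person; map thresholds p<.01 to .001.

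**Assumed:** 30 HC and 30 MCI, all scanned (the best case under the cap); one region; one-sided tests; true HC-MCI gap d of 0.5 or 0.8 SD, identical in both sessions (no tDCS effect); between-session correlation r of 0.7 to 0.3; equal variances; no period or carry-over effect.

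**Step 1. Chance of missing a real gap in one map.** The group t statistic has 58 degrees of freedom and noncentrality d × √(n/2).
- d = 0.5: 0.5 × √15 = 1.94. Against critical values of 2.39 (p<.01) and 3.24 (p<.001), the miss rates are 67% and 89%.
- d = 0.8: 0.8 × √15 = 3.10. The miss rates are 24% and 55%.
- With 20 per group and d = 0.5, the miss rates are 79% and 95%.

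**Step 2. Chance of the sham-only pattern with no tDCS effect.** The two t statistics were simulated jointly with correlation r. Ranges run from r = 0.7 to r = 0.3.

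| True gap | Threshold | Non-significant under active, given significant under sham | Pattern among all such regions |
|---|---|---|---|
| 0.5 SD | .01 | 35-55% | 12-18% |
| 0.5 SD | .001 | 54-78% | 6-8% |
| 0.8 SD | .01 | 13-20% | 10-15% |
| 0.8 SD | .001 | 29-45% | 13-20% |

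The last column is the third column multiplied by the chance of significance under sham. For example, at 0.5 SD, p<.01 and r = 0.3: 0.33 × 0.55 = 0.18.

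**Step 3. Regression to the mean.** At d = 0.5, p<.001 and r = 0.5, regions that pass under sham show an average observed sham gap of 0.92 SD. The expected active gap in those regions is 0.5 + 0.5 × (0.92 − 0.5) = 0.71 SD. The apparent closure of 0.21 SD is produced by selection alone.

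**Step 4. Effect on a test of MCI change.** Suppose MCI active minus sham were tested (two-sided .05, so 2.5% in the favourable direction) only in regions that passed the sham map. With no effect, the simulated false-positive rate is about 3-8% across the scenarios of Step 2. If regions are chosen on the HC > MCI contrast averaged over active and sham, it is about 2.5%. The reason is that cov((A+S)/2, A−S) = (var A − var S)/2, which is zero when the two sessions have equal variance.

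**Step 5. What a non-significant active gap leaves open.** The 95% half-width for a group difference is 1.96 × √(2/30) = 0.51 SD with 30 per group and 1.96 × √(2/20) = 0.62 SD with 20. A moderate remaining gap cannot be excluded.

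**The case against.** The strongest reply is that the plan never says absence from the active map means restoration. It says the contrasts will help clarify the question, and it labels them exploratory. That is correct. A reader might infer that non-significance will be read as normalisation, or that the plan has no other evidence on restoration. The documents support neither reading. The within-MCI active > sham contrast, the mixed ANOVA and Aim 2's comparison of BOLD change all bear on the question.

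This affects the size of the problem. If a restoration claim also required the MCI active > sham contrast to pass at the same map threshold, the conditional rate at 0.5 SD would fall from 35-55% to about 2% or less at p<.01, and from 54-78% to 0.5% or less at p<.001. With that contrast at one-sided .025, it would be 3-8%. But the plan does not state this conjunction either. It attaches the restoration conclusion to the two between-group maps and to nothing else.

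The selection argument is also conditional. The a priori ROIs and the task main-effect mask are not chosen on the sham gap, and nothing says the MCI change will be tested only in sham-selected regions. Step 4 shows what would happen if it were.

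Finally, even a clear MCI change, or a group-by-stimulation interaction, would not show normalisation without an estimate of what gap remains. That part of the concern is untouched.

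**Conclusion.** The point holds in a limited form. The two contrasts that the plan assigns to the restoration question cannot answer it, and the only pattern within them that suggests restoration arises often enough with no effect to mislead: about 6-20% of regions with a true 0.5- or 0.8-SD gap, and 13-78% of those that were significant under sham. These figures rest on assumed group sizes, gap sizes and correlations and apply to a single region. They describe the pair of maps read alone, not the whole plan.

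It would go too far to say that a missed gap under active is the expected result whatever the true gap. At 0.8 SD and p<.01 the miss rate is 24%. It would also go too far to say that the trial is bound to report a false restoration.

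What is missing is a definition of restoration and a link from that conclusion to the analyses that measure change. Severity is modest, because the analysis is exploratory and the repair is almost free.

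**What to change.** In the between-group paragraph at the end of the statistical section, replace the joint reading of the two maps with the following.

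1. Take the regions from the a priori ROIs already listed under Task analysis, or from the HC > MCI contrast averaged over active and sham. Do not take them from the sham map.
2. In those regions, report the MCI active-minus-sham change and the residual gap between HC under sham and MCI under active, each with a 95% confidence interval. Reconcile this with Aim 2 by stating which contrast is the between-group comparison of BOLD change.
3. State that absence of a region from the HC active > MCI active map is not evidence of restoration. Use the word restores only where the interval for the MCI change, signed towards closing the gap, lies above zero, and always alongside the residual-gap interval. If a margin for the residual gap is wanted, fix it before the data are seen and do not set it as a fraction of the observed gap.

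The cost is a few sentences and a few extra contrasts on scans already planned, with no new participants or procedures. The downside is that fewer regions will support a restoration statement. With a residual-gap interval of about ±0.5 SD at 30 per group, the honest answer will often be that restoration was not shown.
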